Management of Sub-Clinical Bacteriuria in Pregnancy: A Feasibility Trial

NCT03275623

Version Date: 08/22/2017

Management of Sub-Clinical Bacteriuria in Pregnancy: A Feasibility Trial

[name]
[name]
[name]
[name]

Background:

Bacterial Colonization in the Urine

Assessment and treatment of bacterial colonization in the urine during pregnancy is a routine part of prenatal care.¹ A urinary tract infection (**UTI**) is defined as urine culture colonization >100,000 (**10⁵**) colony forming units (**CFU**) of bacteria per ml with signs and symptoms of UTI including dysuria, frequency, urgency, suprapubic pain, and/or hematuria.¹⁻³ Asymptomatic bacteriuria (**ASB**) is defined as urine culture colonization > 10⁵ CFU in the absence of signs and symptoms of UTI, and occurs in 2-10% of pregnancies.^{3,4} Pregnant women with a UTI or ASB are routinely prescribed antimicrobial therapy based on identified organisms and sensitivities.

Sub-Clinical Bacteriuria

Sub-clinical bacteriuria (**SCB**) occurs when urine culture colonization is between 1 - 10⁵ CFU. The frequency by which SCB occurs in pregnancy is unknown. It is also unknown the rate of progression from SCB to UTI and/or ASB, and subsequently development in to pyelonephritis. Moreover, there are no current guidelines that direct management in this particular condition in pregnancy. In current clinical practice, there is strong variation in care such that many patients are treated, despite the lack of proven benefit while other clinicians do not treat.

[figure not shown]

Figure 1. Schematic of potential progression of bacterial colonization in the urine.

Clinical Importance

Bacterial colonization in the urine during pregnancy can lead to adverse maternal and neonatal outcomes. Pyelonephritis is the primary concern in pregnancy due to its association with potential urosepsis, renal abscess, decline in renal function, preterm labor and preterm birth.⁵ Although untreated

UTI is the greatest risk factor for developing pyelonephritis, ASB can also lead to pyelonephritis. In a recent randomized controlled trial of 4200 women in the Netherlands, they report that the incidence of pyelonephritis is only 2.4% when ASB is untreated compared to 0.6% when treated.⁶ With such a low incidence, there is new debate whether to treat or expectantly manage ASB. This same debate also pertains SCB. It is unknown whether treatment or expectant management of SCB will lead to difference in the rate of progression to UTI and/or SCB, and ultimately pyelonephritis.

Risk of Antimicrobial Therapy

The two main risks of empiric antimicrobial therapy include potential for adverse drug effects and contribution to drug resistance. The use of antibiotics is not benign especially during pregnancy. Adverse drug effects include masking a diagnosis with empiric treatment of symptoms and no identification of an organism. Often times the diagnosis maybe correct, but the antibiotic that was chosen for treatment does not have sufficient coverage of the organism that is causing the infection. Common side effects to routinely used antibiotics such as nitrofurantoin, sulfa, amoxicillin and cephalixin includes rash and diarrhea.⁹⁻¹⁰ The rise in antibiotic resistance over the past decades is evidence to the clinical consequences of unnecessary antimicrobial treatment across the disciplines in medicine. Such consequences also have been evident in the field of obstetrics. Nearly 50% of urinary isolates are resistant to routine ambulatory antibiotic therapy. Zhanel et al. looked at resistance to treatment in the NAUTICA trial. The goal of the North American Urinary Tract Infection Collaborative Alliance (NAUTICA) study was to determine antibiotic susceptibility to commonly used agents for urinary tract infections against outpatient urinary isolates obtained in various geographic regions in the USA and Canada. This study reports higher rates of antibiotic resistance in US versus Canadian outpatient urinary isolates and demonstrates the continuing evolution of resistance to antimicrobial agents.⁷ Thus, if antibiotic therapy is not necessary for the management of subclinical cystitis due to low incidence of progression to pyelonephritis, it should not be prescribed.

Gap in Knowledge

The gap in knowledge is whether the risks and benefits of empiric treatment with antimicrobial therapy for treatment of SCB outweigh the risk and benefits of developing UTI, ASB or pyelonephritis from expectant management or no treatment of SCB.

Rationale for this clinical trial

The rationale for this clinical trial is to determine if treatment of urine cultures with organisms of 1 – 100,000 CFU are beneficial to pregnancy outcomes when obtained at routine prenatal clinic visits. In current clinical practice, there is a strong variation in care such that many patients are treated for urine cultures with organisms of $<10^5$ CFU despite the lack of proven benefit while other clinicians do not treat.

If it is found that treatment of urine cultures with 1 - 10^5 CFU impact clinical care of a pregnant patient by decreasing adverse pregnancy outcome, guidelines will need to be modified to include treatment recommendations of urine cultures that do not currently meet criteria of a urinary tract infection. On the other hand, if there is no benefit to treatment of urine cultures 1 - 10^5 CFU, then unnecessary antibiotics could be avoided thereby potentially reducing unknown adverse effects to these drugs or resistance to antibiotics, which continues to be an alarming health challenge.

Hypothesis:

We hypothesize that treating urine cultures with organisms between 1- 10^5 CFU grown in culture media in a pregnant population leads to improvement of pregnancy outcomes.

Objectives:

To determine the rate of progression from SCB to either UTI or ASB with antimicrobial treatment of urine cultures with organisms of $1-10^5$ CFU compared to no treatment at prenatal care clinic visits.

Study Design:

For this pilot study, we propose a feasibility trial to determine if a randomized control trial for the treatment of subclinical cystitis to prevent pyelonephritis and culture proven cystitis. The trial will investigate the effects of treatment or non-treatment of urine cultures obtained during prenatal care visits prompted by a positive urinalysis or symptoms, and determine if a randomized control trial is needed to further investigate outcomes.

Patients meeting clinical indications will have a urine culture ordered due to two reasons: a) symptoms of a UTI or b) positive UA suspicious for infection/inflammation. A negative urine analysis is defined as an analysis that is negative for bacteria, leukocyte esterase, nitrites, and protein. A negative urine culture is defined as no growth or any amount of skin flora only.

Inclusion Criteria:

We will include pregnant women who seek prenatal care within the University of Texas Health System with UT Physicians.

Exclusion Criteria:

We will exclude women:

- Less than 18 years of age
- Risk factors to complicated UTI (including but not limited to: diverticula, urolithiasis, renal cysts, indwelling catheter, intermittent catheterization, stent placements, nephrostomy tubes, neurogenic bladder, cystocele, vesicoureteral reflux, ileal conduit)⁸
- Use of immunosuppressant drugs
- Abnormalities of the urinary tract (including but not limited to: known ureteric or urethral strictures, tumors of the urinary tract, pelvicalyceal obstruction, congenital anomalies, history of urological procedures)
- History of renal disease including renal failure and transplants
- Urine culture $> 10^5$ CFU of any organism

Those with a urine culture for bacteria but $1-10^5$ CFU will be randomized to one of two management plans:

1. Prenatal care with treatment for any urine culture with growth of $1-10^5$ CFU of any organism
2. Prenatal care without treatment for any urine culture with growth of $1-10^5$ CFU of any organism

Randomization:

Randomization will be performed based on a computer-generated list that will be created by a non-clinical member of the research team. Randomization will be stratified by clinic site. A permuted block randomization with a random fashion will be used to prevent imbalances between sites. At subsequent clinic visits, clinic staff will continue to obtain urine culture from symptomatic patients or patients where further work up of a urine culture is warranted. 'Physician to treat urine culture with $1-100,000 (10^5)$ CFU" or 'Physician to NOT treat urine culture with $1-100,000 (10^5)$ CFU", based on the computer-

generated list, stored on the RedCap database. The research nurses and team may access the RedCap database from any clinical site.

Methods:

At the initial prenatal care clinic visit all pregnant women will have their urine screened with a UA and urine culture. Patients meeting inclusion criteria will be approached for randomization.

Those with a urine culture positive for bacteria 1- 10x5 CFU will be randomized to treatment or no treatment.

Those randomized to NO treatment will have a test of cure performed three weeks after initial negative urine culture or at next clinical visit thereafter.

Those randomized for treatment will be prescribed the most commonly used antibiotic for urinary tract infections in pregnancy. This includes: Nitrofurantoin, Cephalexin, and Amoxicillin. It is unsure which antibiotic the participant will receive but a majority of the time it will be one of the above named antibiotic. The choice will be determined by the physician, but will accommodate participants' prior medication history and adverse events.

Treatment will continue with a test of cure (urine culture performed after treatment with antibiotics) after each round of antibiotic until the urine culture shows no growth of bacteria and/or shows any amount of skin flora only.

Written, informed consent will be obtained by a member of our research team, either a physician or research assistant.

Once the patient is randomized to their designated arm, urine cultures will continue to be collected throughout prenatal care visits as clinically indicated.

[figure not shown]

Figure 2. Flow diagram of study

Primary Outcome:

The incidence of cystitis defined as a urine culture with $>10^5$ at any point during antenatal care in this pregnancy population and the incidence of pyelonephritis.

Data Collection:

Data will be collected using standardized forms regarding maternal demographics, pregnancy characteristics, laboratory tests ordered in response to clinical signs or symptoms, medications prescribed and/or administered, and maternal/fetal adverse effects. Information for these forms will be obtained from UTPB and Bellaire clinical schedule, Care4 and AllScripts. The standardized forms that will be used during the study have been developed and approved by the Department of Obstetrics, Gynecology, and Reproductive Sciences for the purposes of uniform data collection of Internal Review Board approved studies being conducted.

Sample Size:

Because this is a feasibility trial, 50 patients will be recruited from all clinical sites. 25 patients will be randomized to prenatal care with treatment for any urine culture with growth between $1-10^5$ CFU of any organism and 25 patients will be randomized to prenatal care without treatment for any urine culture with growth between $1-10^5$ CFU of any organism. Recruitment will be stopped after recruitment of 50 randomized patients or a 10-month time period whichever is completed first.

Data Analysis

Chi-square tests will be used to compare categorical data between the two treatment groups. Student's t-test will be used to compare numerical data. The rate of progression to SCB, UTI, or pyelonephritis will be determined by clinical findings, diagnosis if admitted to the hospital and laboratory/urine culture results meeting criteria for those mentioned above.

Procedures to Maintain Confidentiality

All information and data will be kept on paper research charts that will be stored in a locked file cabinet within a locked research office of our research team/research coordinator. In addition, an electronic database of information and data will be stored on the computer of our research coordinator that is password protected, and in a locked office of the research coordinator. We will record subject information only by study code number.

Potential Benefits and Risks

There are potential risks and benefits to either treatment strategy. Since treatment or no treatment are currently both generally accepted standard of care options, providers, based on their personal preference and practice style, may choose to treat or not. Potential benefits of antibiotic treatment of those with $1-10^5$ CFU in urine culture may be decreased development of UTI, pyelonephritis, PTL, and preterm birth. Potential risks of treatment may be side effects of the medications as well as potential untoward effects of antibiotic therapy that may increase development of resistant organisms in urine and other locations (e.g. vaginal, cervix, gut) or may lead to change in flora (e.g. vaginal, cervix, gut) which may increase risk of adverse pregnancy outcomes. The benefits of no treatment may be to avoid unnecessary and unindicated antibiotic therapy. If evidence shows that treatment of this subset of

pregnant patients decreases adverse pregnancy outcome, this can leave a lasting impact on how we treat urinary tract infections in pregnancy.

References

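### The feasibility trial is meant to inform whether an RCT is needed, but it names no feasibility outcome, lists no screening or consent counts, and ties no result to that decision

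*Combined protocol and SAP*

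**What the plan says.** The title and the Study Design and Sample Size sections call this a feasibility or pilot trial. Two sentences in Study Design give its purpose. The first has no predicate: the trial is "to determine if a randomized control trial for the treatment of subclinical cystitis to prevent pyelonephritis and culture proven cystitis", and the sentence ends there. The second says the trial will study the effects of treating or not treating, and "determine if a randomized control trial is needed to further investigate outcomes".

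The other sections bearing on that purpose read as follows.

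- **Hypothesis and Objectives:** the hypothesis is one of efficacy. The objective is the rate of progression with and without treatment.
- **Primary Outcome:** culture-defined cystitis "at any point during antenatal care in this pregnancy population and the incidence of pyelonephritis". No other outcome is named.
- **Data Collection:** demographics, pregnancy characteristics, "laboratory tests ordered in response to clinical signs or symptoms", medications and adverse effects. Counts of women screened, eligible, approached, consenting or declining are not listed.
- **Sample Size:** "Because this is a feasibility trial, 50 patients will be recruited from all clinical sites", 25 to each arm. Recruitment stops at 50 randomised women or at 10 months, whichever comes first.
- **Data Analysis:** chi-square and t-tests between arms. This section also says that progression rates will be determined from clinical findings, hospital diagnoses and culture results. It gives no interval and no rule for using those rates.

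**The concern.** A feasibility trial earns its size by informing a later decision. Here the decision is named, but nothing in the plan leads to it. Neither a significant nor a non-significant chi-square result is assigned a consequence for a later RCT, and no recruitment, consent, adherence or follow-up figure is named that would show whether such a trial could be run.

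Two things are at stake. First, consent and screening denominators may not be recoverable afterwards if nobody logs them at the time. Second, a non-significant comparison could be taken as absence of benefit. The Rationale section already says that a finding of no benefit would support withholding antibiotics, so the route to that misreading is short.

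**Working it through.** **Inputs from the documents.** At most 25 per arm (Sample Size). Pyelonephritis 2.4% untreated and 0.6% treated in asymptomatic bacteriuria (Clinical Importance). The progression rate in sub-clinical bacteriuria is stated to be unknown.

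**Assumptions.** Two-sided 5%, since no alpha is stated. The asymptomatic-bacteriuria rates serve as a proxy for sub-clinical bacteriuria. For cystitis, treatment halves an untreated rate somewhere between 10% and 50%.

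**The plan's own figure.** N = 50 cannot be reproduced, because no alpha, power, event rate, effect size, precision target or dropout is given. It cannot be called arithmetically wrong either.

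**Step 1: pyelonephritis.**
- Expected events: 25 × 0.024 + 25 × 0.006 = 0.75 in the whole trial.
- Chance of none in either arm: 0.976^25 × 0.994^25 = 0.545 × 0.860 = 0.469, or 47%.
- With 25 per arm, chi-square = (a − b)² × 50 / [(a + b)(50 − a − b)]. For 3 events against 0 it is 9 × 50 / (3 × 47) = 3.19, below 3.84. For 4 against 0 it is 16 × 50 / (4 × 46) = 4.35. At least four untreated cases with none treated are therefore needed for significance.
- Exact enumeration over all outcomes gives power of 0.2%.

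**Step 2: cystitis.** Exact enumeration, 25 per arm. The Data Analysis section does not say whether the chi-square is continuity-corrected.

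| Untreated vs treated | Uncorrected | Yates-corrected |
|---|---|---|
| 10% vs 5% | 8% | 1% |
| 20% vs 10% | 17% | 6% |
| 30% vs 15% | 26% | 14% |
| 40% vs 20% | 35% | 23% |
| 50% vs 25% | 48% | 36% |
| 60% vs 30% | 62% | 51% |

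For a halving, non-significance is the likelier result up to an untreated rate of 50%. Somewhat above that, uncorrected power passes one half. Stopping at 10 months with fewer women lowers every figure.

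**Step 3: what 25 untreated women can estimate.** Exact (Clopper-Pearson) limits:
- 0/25: two-sided 95% upper limit 1 − 0.025^(1/25) = 13.7%; one-sided 95% upper limit 1 − 0.05^(1/25) = 11.3%.
- An assumed 5/25: 6.8% to 40.7%. With n = [1.96√(2p̄(1−p̄)) + 0.84√(p₁(1−p₁) + p₂(1−p₂))]² / (p₁ − p₂)², p₂ = p₁/2 and p̄ the mean of the two rates, a later RCT at 80% power needs 653, 199 or 80 per arm at the lower limit, the estimate and the upper limit.

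The untreated rate is therefore useful for planning, but only with its interval and a rule for using it.

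**Step 4: feasibility measures.** Adherence and follow-up culture completion mean different things in the two arms, so the denominator is 25. An assumed 20/25 gives 59% to 93%. Accrual of 50 in 10 months is 50/10 = 5 per month. This is derived from the stopping rule; the plan does not state it as a target.

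**The case against.** The best defence is that the plan judges need from clinical effects. The complete Study Design sentence says so, the progression rate is unknown, and the Data Analysis section commits to determining it. On that view the trial already has its planning estimate, and operational measures are an outside standard. Much of this stands: estimating progression is a legitimate pilot aim, and there is no ground for requiring operational measures to displace the clinical primary outcome. What remains is that the estimate has no interval and no stated use, and that the sentence which might have posed the operational question is unfinished.

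The 50-women or 10-month limit might be offered as a feasibility measure. It would yield crude accrual, but it only ends enrolment and carries no target or consequence.

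Three stronger readings are tempting, and the documents do not support them.

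- **That the trial collects no screening or consent data.** The standardised forms and Figure 2 are not available here, and consent is obtained in writing. One can say only that the Data Collection section lists no such counts.
- **That 50 is too few.** A feasibility trial without a power calculation is not an error. The power figures show what the between-arm test can bear; the gap would exist without them.
- **That the trial could never show a difference.** With high untreated rates or very large effects on cystitis it could.

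**Conclusion.** The point holds as a design gap that should be corrected. The plan sets a decision, names only clinical outcomes, lists none of the counts behind consent or yield, and attaches no result to the decision. Followed as written, the decision would rest on a comparison unlikely to settle it: a 47% chance of no pyelonephritis at all, and 8% to 48% power for a halving of cystitis (1% to 36% if continuity-corrected).

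Those figures depend on the proxy rates, the assumed halving, the assumed 5% level and full recruitment. The gap itself depends on none of them; it follows from the text, with the reservation that the forms and Figure 2 are unseen.

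**What to change.** 1. **Aim.** Complete the unfinished Study Design sentence, separating whether an RCT can be run from whether it is needed.
2. **Can it be run?** Keep a de-identified log of women cultured, with sub-clinical bacteriuria, eligible, approached and consented. Beside the existing clinical outcome, add feasibility outcomes with exact 95% confidence intervals: women randomised per month, consent among eligible women, and, by arm, adherence to allocation and follow-up culture completion. The sponsor sets proceed, modify and stop thresholds in advance, spaced to suit each denominator.
3. **Is it needed?** Report cystitis and pyelonephritis rates per arm, and their difference, with 95% confidence intervals as the main results in place of reliance on the chi-square test. State in advance how the untreated rate and its interval will inform whether a later RCT is run and at what size. If a rule uses an upper limit, say whether it is one-sided or two-sided, since even 0/25 leaves 11.3% or 13.7%.
4. **Interpretation.** State that a non-significant difference will not be read as no benefit or as no need for an RCT.

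**Cost.** Amendment wording, a log covering women who do not enrol, and data-handling text for it. No additional patients. The downside is that no efficacy conclusion can be drawn from this trial.

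Two separate contradictions affect these measures, and the passages must be reconciled. The Methods section says "At the initial prenatal care clinic visit all pregnant women will have their urine screened with a UA and urine culture", while Study Design says "Patients meeting clinical indications will have a urine culture ordered due to two reasons" (symptoms or a positive urinalysis); this bears on the denominator for yield. Methods also gives the untreated arm "a test of cure performed three weeks after initial negative urine culture", although randomised women have growth; this bears on follow-up completion.

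### Beyond an early test of cure that differs by arm, cultures are clinically triggered, so later asymptomatic bacteriuria is incompletely counted and the progression rate is biased low

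*Combined protocol and SAP*

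**What the plan says.** - **Objectives:** "To determine the rate of progression from SCB to either UTI or ASB", compared between treatment and no treatment.
- **Background, Bacterial Colonization in the Urine:** ASB is growth above 10^5 CFU "in the absence of signs and symptoms of UTI".
- **Primary Outcome:** a culture above 10^5 "at any point during antenatal care in this pregnancy population and the incidence of pyelonephritis". Symptoms are not required.
- **Study Design:** a culture is ordered for symptoms or for a urinalysis suspicious for infection or inflammation.
- **Randomization:** at later visits "clinic staff will continue to obtain urine culture from symptomatic patients or patients where further work up of a urine culture is warranted".
- **Methods:** every woman has a urinalysis and culture at the first prenatal visit. After randomization "urine cultures will continue to be collected throughout prenatal care visits as clinically indicated".
- **Methods, scheduled tests after entry:** the no-treatment arm has one test of cure at three weeks or the next visit after that. The treatment arm has a culture after each antibiotic round, repeated until negative. Neither depends on symptoms.
- **Data Collection:** the laboratory item covers tests prompted by signs or symptoms. Scheduled tests are not mentioned.

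Nothing further is scheduled, and no section says how often urinalysis is repeated.

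**The concern.** ASB can be found only by culturing a woman who has no symptoms. The plan ensures this once, early, in the no-treatment arm, and for as long as cultures stay positive in the treatment arm. For the rest of pregnancy it depends on a positive urinalysis or on clinical judgement. A woman who becomes bacteriuric without symptoms in that period and is not cultured has no event under the outcome definition, so she counts as not progressed.

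Two results are at stake. The first is the rate itself. The Background says the rate of progression from SCB is unknown, estimating it is the objective, and Study Design will use the pilot to judge whether a randomized trial is needed. The second is the comparison. The number of scheduled looks differs by arm and, under treatment, depends on the results. Physicians are also told whether to treat, so decisions about further work-up can differ by arm.

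Pyelonephritis is little affected, because Data Analysis also relies on clinical findings and admission diagnoses.

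**Working it through.** **Plan's own figure.** The only figure is the sample size: 25 + 25 = 50, which is consistent. It is a fixed feasibility number with no error rate, power or expected rate, so there is no power calculation to reproduce.

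**Model.** The documents give none of the inputs below; all are assumptions.

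- s = share of progressions that are symptomatic (all of these assumed to be cultured)
- t = share of asymptomatic progressions caught at a scheduled test of cure
- d = share of the remaining asymptomatic progressions caught by a culture prompted by urinalysis or clinical judgement

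Share detected = s + (1 - s) x [t + (1 - t) x d].

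**Overall rate, true value 20% (5 of 25), s = 0.5**

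| t | d | Share detected | Observed rate | Seen of 25 |
|---|---|---|---|---|
| 0.25 | 0.25 | 0.5 + 0.5 x (0.25 + 0.75 x 0.25) = 0.719 | 14.4% | 3.6 |
| 0.50 | 0.50 | 0.5 + 0.5 x (0.50 + 0.50 x 0.50) = 0.875 | 17.5% | 4.4 |

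**Range.** At s = 0.25, t = d = 0, detection is 25%. At s = t = d = 0.75 it is 0.75 + 0.25 x (0.75 + 0.25 x 0.75) = 98%. The direction is the same throughout; the size is not determined.

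**Comparison, equal true rates of 20%, s = 0.5**

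1. More is caught at scheduled tests under treatment (d = 0.25 in both arms; t = 0.25 untreated, 0.50 treated). Untreated: 14.4%. Treated: 20% x [0.5 + 0.5 x (0.50 + 0.50 x 0.25)] = 20% x 0.8125 = 16.3%. This is a spurious 1.9 points against treatment. With t = 0.75 in the treated arm, 20% x 0.906 = 18.1%, a spurious 3.75 points.
2. Fewer indicated cultures under treatment (t = 0.25 in both arms; d = 0.25 untreated, 0 treated). Untreated: 14.4%. Treated: 20% x (0.5 + 0.5 x 0.25) = 20% x 0.625 = 12.5%. This is a spurious 1.9 points in favour of treatment.

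The bias can therefore run either way.

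**The case against.** **Later ASB may be caught well enough.** Both arms have a test of cure regardless of symptoms, and a positive urinalysis is a stated reason for culture. Under Study Design a negative urinalysis must be free of bacteria, leukocyte esterase, nitrites and protein, so a symptom-free woman can readily qualify for a culture. Figure 2, the flow diagram, was not available for this check. All this stands as a limit on size. It does not close the gap, because the visible text schedules neither a culture nor a urinalysis after the test of cure.

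**It is a pilot of 50 women.** Even 5 of 25 has an exact 95% interval of about 7-41%, wider than the illustrated distortion. That is true, but a wide interval around a mislabelled rate does not correct the label, and the rate is the stated objective.

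A reader might also infer three stronger points, which the documents do not support:

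- *That cultures follow symptoms alone and ASB is largely unseen.* The tests of cure and the urinalysis route contradict the first part. The second holds only if both t and d are small, which is not shown.
- *That treatment will look falsely beneficial because antibiotics mask disease.* The Background's remark on "masking a diagnosis with empiric treatment of symptoms and no identification of an organism" concerns empiric treatment without a culture result. Here every randomized woman has a culture with growth. The visible asymmetry, repeat cultures under treatment, runs the other way.
- *That the later trial will be mis-sized by a known amount.* For 80% power at two-sided 5% (unpooled normal approximation), detecting a halving needs 197 per arm from 20%, and about 288 or 230 from 14.4% or 17.5%. The difference is an error only if the later trial ascertains more completely than this one, and the plan does not say that the trial will be powered on this rate.

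**Conclusion.** The point holds in a limited form. After an early test of cure whose timing and number differ by arm, symptom-free bacteriuria is found only when a culture is prompted, although the outcome window is all of antenatal care. The reported rate of progression to UTI or ASB is therefore biased low whenever some asymptomatic progression falls outside the scheduled and prompted cultures. The unequal looks can also bias the comparison in either direction.

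The amount cannot be computed from the documents. The fall from 20% to about 14-17.5% rests on assumed values of s, t and d and is an illustration, not an estimate. The point warrants a change because the plan, followed exactly, would report a figure under a name it does not earn, and the correction is small.

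**What to change.** 1. **Primary Outcome and Data Analysis:** keep the outcome (any culture above 10^5, and pyelonephritis), label it clinically detected, and do not call it the rate of progression to ASB.
2. **Data Collection:** record the trigger of every post-entry culture (scheduled test of cure, symptoms, urinalysis, other), and state that scheduled tests are captured.
3. **Data Analysis:** report events by trigger, and the number of cultures per woman by arm.
4. **Data Analysis:** add a comparison restricted to each woman's first scheduled post-entry test, so that both arms have one look regardless of symptoms. State whether the no-treatment test is a culture; Methods says so expressly only for the treatment arm.
5. **Reconcile the text:** Methods times the no-treatment test from an initial negative culture, yet these women are randomized on a culture with growth. The sponsor must settle which is meant.

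The cost is one form field, a little more analysis and a narrower conclusion. The first-test comparison equalises the number of looks but not their timing, and covers only one early time point. A common later culture for every woman would add ascertainment (about 50 cultures), but it is an added procedure, and the point does not depend on it.

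### Does storing the randomisation list on a shared RedCap database mean that recruiting staff can see the next assignment?

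*Combined protocol and SAP*

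**What the plan says.** Three statements in the Randomization section matter. On generation: "Randomization will be performed based on a computer-generated list that will be created by a non-clinical member of the research team". On the method: "A permuted block randomization with a random fashion will be used to prevent imbalances between sites", with stratification by clinic site. No block size is given, and it is unclear whether the random element refers to varying block sizes.

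On storage and access, the section first turns to follow-up: "At subsequent clinic visits, clinic staff will continue to obtain urine culture from symptomatic patients", or from others who need further work-up. It then gives the two alternative instructions to the physician (treat, or do not treat, cultures in the study range) and says that they are based on the computer-"generated list, stored on the RedCap database. The research nurses and team may access the RedCap database from any clinical site".

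On entry, the Methods section says: "Patients meeting inclusion criteria will be approached for randomization". It next states that women whose culture falls in the study range are randomised, and later adds: "Written, informed consent will be obtained by a member of our research team, either a physician or research assistant".

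The text supplied has no sentence on hiding unused assignments, on withholding block sizes, or on releasing an assignment only once eligibility and consent are recorded. Figure 2, the flow diagram, is not reproduced there and cannot be checked.

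**The concern.** A non-clinical list creator protects how the sequence is made, not who sees it afterwards. If the list is on a database that the research nurses and team can open, and a member of that team takes consent, the people who enrol women might know the next arm before deciding whom to enter, or when.

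The setting makes this worth asking. The comparison is treatment against no treatment, and the physician is told the arm. The section on benefits and risks says that providers differ by preference on whether to treat. There is also some discretion at entry: two exclusion criteria are open lists, one of them beginning "Risk factors to complicated UTI (including but not limited to". A woman could in principle be judged ineligible after the next arm was known.

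At stake would be the between-arm comparison, for which the Data Analysis section plans chi-square tests. According to the Study Design section, the trial is also meant to "determine if a randomized control trial is needed to further investigate outcomes".

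**Working it through.** The plan gives no figure on concealment to reproduce. Its only related arithmetic, 25 + 25 = 50 women (Sample Size section), is consistent. The check is therefore mainly one of reading.

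**What the storage sentence covers.**
- The sentence has no main verb. Its subject is the pair of physician instructions, and the list is what those instructions are based on. What is stored may be the whole list or each woman's instruction; the grammar does not settle it.
- The sentence before it concerns cultures at later visits. Both arms, as defined after the exclusion criteria, apply to any culture in the study range, so the instruction continues to apply after entry. Staff who see an enrolled woman again, possibly at another site, need to look up her arm. That need is enough to explain access from any clinical site.
- The text says that staff may access the database. It does not say that they may view the unused part of the list. Access to a database need not carry a right to view every record in it.

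**What foreknowledge would need in order to act.** Staff would have to be able to see unused assignments, look at them, hold a preference, and then act on it when approaching, consenting or excluding women. The documents establish none of these for recruiting staff; the remark on preference describes providers in general. The Methods section mentions the approach to women who meet the inclusion criteria just before it mentions randomisation on the culture result. The only inclusion criterion is prenatal care within the health system. This order suggests, without proving, that women are approached before the qualifying result is known. The colony count that decides entry is a laboratory result.

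**Leverage if it did happen (illustration only).** Inputs: 25 per arm (Sample Size section); no treatment effect (assumed); a gap *g* in progression risk between higher-risk and lower-risk women of 10, 20 or 30 points (assumed); *k* one-for-one exchanges between arms (assumed).

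- Shift in case-mix difference per exchange: 2/25 = 0.08, or 8 percentage points.
- Shift in risk difference: (2k/25) × g.
- k = 1: 0.08 × 10, 20, 30 = 0.8, 1.6, 2.4 points.
- k = 5 (10 of the 50 women): 0.40 × 10, 20, 30 = 4, 8, 12 points.
- Standard error of the risk difference at common risk *p* (assumed): √(2p(1 − p)/25). At p = 0.10, √0.0072 = 0.085, or 8.5 points. At p = 0.20, √0.0128 = 0.113, or 11.3 points.

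One exchange is thus at most 2.4/8.5 = 0.28 of a standard error. Five exchanges give 4 to 12 points, which reaches the size of the standard error only towards the upper end of the assumed gaps. One-for-one exchange is itself a stylised model, since rejecting or deferring a woman would be the more likely route.

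**The case for a change.** The strongest case for a change is that the omission is real on either reading. If the list itself is open, foreknowledge is permitted; if only enrolled women's arms are visible, the text still does not say so. The non-clinical list creator does not cure this, and varying block sizes would not help if the list could be viewed. Nor does the feasibility label dispose of the point, because the protocol states a comparative objective and plans tests between arms. A bias of this kind would not shrink in a larger trial that used the same procedure, and a few sentences would settle the matter at almost no cost.

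Much of this stands. The protocol is silent on concealment, and the safeguards in the confidentiality section (locked storage, a password, study codes) protect participant data rather than the allocation sequence. What does not stand is the step from silence to a defect in the plan. No rule opens unused assignments to recruiters. That a team member takes consent is ordinary practice. The argument about a larger trial concerns a procedure that this protocol does not specify. The low cost of extra wording does not show that the planned procedure is wrong.

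**Conclusion.** No change to the plan follows. This is an undescribed procedure that a sensible database set-up fills: unused assignments hidden, and each arm released after entry and available for look-up at later visits. The wording is compatible with that set-up and arguably points to it. Whether RedCap was configured in this way is a question of fact that the trial team can answer from its set-up, and it would be useful to state in the trial report.

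The documents show no selection bias and give no basis for estimating one. The illustrative shifts of 0.8 to 2.4 points per exchange rest wholly on assumed risk gaps and on the assumption that exchanges occur. A single exchange is well below the chance error of 8.5 to 11.3 points. The conclusion rests on reading the access sentence as look-up of enrolled women's arms, or at least as not granting a view of the unused list. Had the protocol said plainly that recruiters could see upcoming assignments, the conclusion would be different.
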